7. REGULATORY CONSIDERATIONS

In consultation with Novo Nordisk, we have determined that the study will continue to be conducted under an IND. [name], as the current sponsor, will continue to have the IND with the FDA and will comply with all necessary regulations. In the event [name] should leave his position at CCHMC, the newly appointed PI will take over the IND and assume all responsibilities that go with it.

8. RISKS/BENEFITS

The primary benefit of this study is the expected increase in growth rate in individuals treated with GH therapy. Subjects will be provided with a copy of their growth data and growth chart at each visit. Additionally, after each visit, a letter will be sent to the subject's primary care physician detailing the exam findings and laboratory results from that visit. Additionally, this study will provide us additional insights into the clinical presentation of ACAN deficiency which may benefit subjects and their family members in the future.

The major risks from this trial are related to the treatment with GH itself. Known side effects of this FDA-approved medication include mild edema, intracranial hypertension, slipped capital femoral epiphysis (SCFE), progression of scoliosis, and injection site reactions.

- Edema: Edema is usually mild and self resolves. Subjects will be asked about foot swelling. If edema persists and is painful, the dose of GH will be decreased 10-20%. If the edema continues to persist 2 weeks after decreasing the dose and is impacting the subject's daily activities, GH will then be discontinued.
- Intracranial hypertension: A funduscopic exam will be performed at baseline and at each follow up visit. In the case of persistent headache +/- blurred vision or vomiting, the patient will be referred to a local ophthalmologist for dilated eye exam to rule out papilledema. If papilledema is present, the subject will then be referred to a local emergency department for further evaluation including lumbar puncture. If papilledema is present, GH will be immediately discontinued. After the complete resolution of all headache symptoms and the complete resolution of papilledema, GH can be restarted at a reduced dose of 30 micrograms/kg/day. If the patient tolerates this dose for 2 months without recurrence of symptoms, then the dose can be increased back to 50 micrograms/kg/day. If at any point papilledema recurs, GH will be permanently discontinued.
- SCFE: A hip exam will be performed at baseline and at each follow up visit. If the patient develops hip or knee pain at any time during the study a hip X-ray will be obtained to rule out SCFE. If SCFE is present, GH will be immediately discontinued.
- Progression of scoliosis: A back exam will be performed at baseline and at each follow up visit. If the patient develops clinically significant scoliosis during the study, the patient will be referred to an orthopedic physician for

further evaluation. The decision whether to discontinue GH will be made in conjunction with the orthopedist depending on the severity of scoliosis. Scoliosis has been reported in a single family with homozygous mutations in the ACAN gene¹⁸. These reported patients had a very severe form of the disease. The subjects in the current clinical trial will all have heterozygous mutations in ACAN. In our report of 103 individuals with heterozygous mutations, scoliosis was not reported in any individual. Additionally, scoliosis usually becomes more evident during puberty and all individuals in this study will be pre-pubertal. Thus, it is highly unlikely that scoliosis will develop during the trial. If it does, we will be unable to determine if the scoliosis is due to the underlying ACAN deficiency or GH treatment.

- Injection Site Reactions: The patients can experience local symptoms related to the subcutaneous administration of GH which include pain at the site of the injection, redness, small bruising, lipoatrophy or lipohypertrophy. Injection site reactions can be avoided by changing the injection site at each injection (injection site rotation).

Radiation risk: Every person is exposed on a daily basis to a certain amount of background radiation originating from soil, rocks, outer space and within the body itself. The amount of radiation for imaging studies varies based on the size of the patient, with children and smaller adolescents being exposed to relatively larger doses of radiation than adults. The average person in Cincinnati receives a radiation dose of about 3 mSv per year. Using the largest exposure estimates for children, the proposed radiology studies would expose the patients to the following amounts of radiation:

- DXA scan (whole body, lumbar spine): approx. 0.013 mSv; four DXA scans: approx. 0.052 mSv
- Bone age (X-ray of the hand): 0.005 mSv; four bone age studies: 0.02 mSv
- Knee X-rays (4 views): 0.001 mSv per view; total 0.004 mSv (for screening visit only, until all 10 patients have been enrolled; afterwards no knee-x-rays are planned for the extension part)

Therefore, total radiation exposure from this study is expected to be 0.08 mSv or less (equivalent to the amount an individual receives over 6 days from background radiation).

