- B. GH initiation – If the subject passes screening, a supply of GH therapy will be shipped to the subject from the study coordinator. The supply amount will be determined by what is needed for the 3 months +/- 2-week window until the next check-in/visit to ensure that subjects do not run out of medication. Receipt of GH will be confirmed via telephone call and the date of GH initiation will be recorded. A log will be provided to the subject to record daily compliance for the first year of treatment with GH.
- C. 1-week telephone call – A telephone call will be made at 1 week (+/- 2 days) to review GH administration and address any issues with medication administration.
- D. 3-month telephone call and remote lab draw – A telephone call will be made at 3 months (+/- 2 weeks) to review compliance and assess for any adverse events that may not have been previously reported (See Adverse Event reporting section). After successful completion of this call, an additional 3 month +/- 2-

week supply of GH will be shipped to the subject. A lab slip will be provided for measurement of IGF-1 level at a local lab. This value is only being used as a safety measure and not as an efficacy outcome measure and thus will not be centralized. It will logically not be possible to centralize this sample.

E. 6-month visit – The subject will return to CCHMC 6 months (+/- 2 weeks) after initiation of GH therapy for a repeat visit. The subject will undergo a routine physical examination including a focused joint exam (inspection of the hip joints, checking for scoliosis) and pubertal staging performed by a pediatric endocrinologist. Vital signs will be obtained. Weight will be measured on a digital scale. Height will be measured in triplicate on a standing stadiometer which is calibrated daily. The average of the three measurements will be used. A funduscopic exam will be performed. Labs will be performed as detailed in **Table 1**. The compliance log will be reviewed, and the subject will be assessed for any adverse events that may not have been previously reported. The dose of GH will be weight adjusted to maintain a dose of 50 micrograms/kg/day. An additional 3 month +/- 2-week supply of GH will be provided to the subject.

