 - f. Frequency of joint complaints.

Study Recruitment

Only study participants that have had a satisfactory response to GH within the first year of treatment will have the opportunity to enroll in the extension trial. This is defined as an increase of height SDS of + 0.3 or greater.

Study protocol

This is an extension trial of rhGH therapy in pre-pubertal children with ACAN deficiency. The primary outcome measures of interest are height velocity and change in height SDS. All patients currently in the treatment trial will continue to receive once daily injections of Norditropin at a standard dose of 50 mcg/kg/day, per initial study protocol (this dose can only be adjusted based on safety guidelines as described in the original protocol for year 1 of therapy, i.e., if IGF-I concentration on therapy is $> +2.5$ SD)

Follow up visits will occur every 6 months, or semi-annually. Study staff will continue to perform check-in calls every 3 months to promote compliance and to record any missed doses, potential new adverse events or use of concomitant medications. In addition, study staff will dispense an additional 3 months of medication and supplies after the 3-month check confirms adequate adherence with the study protocol and no new treatment-related adverse events were reported. Each follow-up visit has a +/-2-week window to accommodate participant schedules and travel. These visits will be the same as previous ones performed for the initial 12-month trial.

The chart below outlines the visit activity schedule **for the extension trial**.

Lab/Assessment	Check-in Calls	18- and 30-Month Visits	24- and 36-Month Visits
Physical exam		X	X
Vital signs		X	X
Height/weight		X	X
TSH		X	X

Free T4		X	X
IGF-I		X	X
IGFBP-3		X	X
Bone Age X-ray			X
DXA scan (whole body, lumbar spine) *			X
Compliance Review	X		
Adverse Event Review	X		
Medication Dispensation	X	X	X

*Additional radiation will be received, approx. 0.013mSv per scan

Only if a participant was unable to complete a study procedure during the initial 12-month trial period due to age, scheduling conflicts, or illness, they may be asked to perform the procedure during the extension trial at one of their scheduled study visits (i.e., MRI, gait assessment, musculoskeletal evaluation).

After each study visit, we will send a letter summarizing the exam findings and lab results to the participant's local primary care physician or pediatric endocrinologist.

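### After intracranial hypertension, the dose may go from 30 back to 50 micrograms/kg/day on absence of symptoms alone, with no eye exam required on the reduced dose (minor, rarely used rule)

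*Combined protocol and SAP*

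**What the plan says.** The combined protocol and SAP, section 8 (Risks/Benefits, intracranial hypertension), sets three conditions for a child in whom papilledema has been found and GH stopped.

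- **Restart at 30 micrograms/kg/day:** "After the complete resolution of all headache symptoms and the complete resolution of papilledema, GH can be restarted at a reduced dose".
- **Return to 50:** "If the patient tolerates this dose for 2 months without recurrence of symptoms, then the dose can be increased back to 50 micrograms/kg/day".
- **Permanent stop:** "If at any point papilledema recurs, GH will be permanently discontinued".

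Eye exams come from two sources. The routine one is in section 8: "A funduscopic exam will be performed at baseline and at each follow up visit". Section 5 repeats it in the text for the 6- and 12-month visits ("A funduscopic exam will be performed"). The extension chart in section 6 has no line for funduscopy, but the text there says "These visits will be the same as previous ones performed for the initial 12-month trial", so I take the exam to continue. The unscheduled one follows persistent headache, with or without blurred vision or vomiting: "the patient will be referred to a local ophthalmologist for dilated eye exam to rule out papilledema".

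On timing, section 6 says "Follow up visits will occur every 6 months, or semi-annually", with a window of 2 weeks either side. Section 5 sets the same spacing and window for year 1. Scheduled contacts between visits are telephone calls.

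**The concern.** Two of the three conditions name papilledema. The one that raises the dose does not. Because the restart condition lists headache symptoms and papilledema separately, the word symptoms in the next step cannot safely be read to cover both.

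The plan does not treat absence of symptoms as enough elsewhere: it examines the fundus of symptom-free children at every follow-up visit. In a child who has already had papilledema on GH, the written rule lets the dose rise before that check is repeated on the reduced dose. A symptom-free recurrence, which under the plan's own rule should end treatment, could then be found only after the child is back on the full dose. The permanent-stop rule does not prevent this, since it acts only once someone has looked and it schedules no exam.

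**Working it through.** The plan gives no figure on this point to reproduce. The check sets the 2-month period against the visit schedule.

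**Inputs.** Doses of 30 and 50 micrograms/kg/day and the 2-month period (section 8); in-person visits every 6 months, each with a window of 2 weeks either side (sections 5 and 6). Two weeks is about 0.46 months.

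1. **Size of the step.** 50/30 − 1 = 66.7%.

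2. **Can the 2 months fall between visits?** Shortest gap: 6 − 2 × 0.46 = 5.08 months. Longest gap: 6 + 2 × 0.46 = 6.92 months. Both exceed 2 months, so the period can always fit between two visits. The point needs only this step.

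3. **How often would it?** Let restart come *r* months after the last visit. With visits exactly 6 months apart, the next is 6 − *r* months after restart, and it falls within the 2 months only if *r* is at least 4.
   - Restart 1 to 3 months after a visit: 100% of periods have no scheduled exam.
   - Restart 4 to 6 months after a visit: 0%.
   - Restart uniform over the 6-month cycle (an assumption): (6 − 2)/6 = 66.7%. A simulation with the visit windows found a visit in 33.4% of periods, so 66.6% had none.

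   The documents do not say how long papilledema takes to resolve, so the range stays 0% to 100%.

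4. **Delay to the next scheduled exam.** Where no exam falls in the 2 months, the child could be on 50 for up to 6 − 2 = 4 months before the next one (6.92 − 2 = 4.92 with windows).

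5. **An exam inside the 2 months may still say little.** If restart comes a week before a visit, the exam reflects one week on 30, and the dose may rise about 7 weeks later with no further look. A sound condition must therefore fix when the exam is done.

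**The case against.** The strongest objection is that the rule may hardly ever operate. Section 5 (Stopping Rules and Dose Reduction Criteria) and section 6 both end treatment after a serious adverse drug reaction. Section 9 counts an event as serious if it may jeopardise the subject and may need intervention to prevent a serious outcome, and as a drug reaction if a causal link is conceivable. Papilledema referred to an emergency department for lumbar puncture, in a child on a drug with this listed side effect, could well meet both tests. This stands, and it narrows the pathway. It does not remove the restart rule, which the sponsor wrote for this event; while that rule remains, its conditions should be complete.

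It is also true that the wording is permissive, so an investigator may examine first; that symptoms bring a dilated exam; and that adverse events are reviewed at the calls. What remains is recurrence without symptoms, between visits, where the investigator chooses not to look. That is a small gap, but nothing in the text closes it.

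A reader might infer more than the documents support:

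- **That GH restarts without regard to papilledema, or that its recurrence is ignored.** Section 8 covers both. The gap is only at the step from 30 to 50.
- **That two thirds of restarted children would go unexamined.** That figure rests on the uniform restart time, which the documents do not supply.
- **That a number of children harmed can be estimated.** The documents give no rate for intracranial hypertension, for its recurrence at 30, or for recurrence without symptoms.

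**Conclusion.** The point holds as a minor, optional safety improvement to a rarely used contingency. The condition for a 67% dose increase is weaker than the plan's own conditions for restarting and for stopping, and the visit schedule does not make up the difference. The conclusion assumes only that the rule is applied as written and that visits are more than 2 months apart, which the schedule guarantees. The share of restarts affected and the number of children at risk cannot be determined from the documents. The treatment trial has 10 children, and only one with resolved papilledema whose treatment had not been ended as a serious adverse drug reaction would reach this step. The primary outcome and the sample-size reasoning are not touched.

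**What to change.** Amend one sentence in section 8 so that the return to 50 micrograms/kg/day requires all of the following:

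- at least 2 months on 30, tolerated;
- no return of symptoms in that time;
- no papilledema on an eye exam done at or after the end of those 2 months and before the dose is increased.

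The exam may be the next scheduled visit funduscopy, which adds no procedure, or the dilated exam by a local ophthalmologist that section 8 already uses.

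**Cost.** If only scheduled visits are used, the longest wait arises when a visit falls just before the 2 months end: up to about 6 months more at 30 (about 6.9 with windows). The dose forgone is 20 of every 50 micrograms/kg/day, so 6 × 20/50 = 2.4 full-dose months, or 6.9 × 20/50 = 2.8 with windows. After a restart later than about month 28, the 2 months end after the 30-month visit. The next scheduled exam is then the 36-month visit, the last in the section 6 chart, so the increase would not happen before then without a local exam. With a local exam at 2 months there is little or no delay, at the price of one extra appointment for that child. The effect on growth cannot be computed, because the documents give no response rate for years 2 and 3.

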9. ADVERSE EVENTS

Subjects will be encouraged to notify the study team immediately should any adverse event occur. Formal review of adverse events will occur at each visit and telephone call as detailed in Table 1. All adverse events will be reported to the IRB, Novo Nordisk and to the FDA as per regulations. An adverse event log will be maintained.

Given that this continues to be a small pilot trial with an anticipated low rate of adverse events, there will be no formal data safety and monitoring board. Rather, [name] or a qualified co-investigator when [name] is unavailable will review

all adverse events within 48 hours and serious adverse events within 24 hours. If a subject requires discontinuation of GH therapy, they will be asked to still complete all follow up assessments up to the 3-year visit.

The study team will comply with all local legal, regulatory, and IRB requirements with regards to adverse events. [name], the sponsor-investigator, will be responsible for reporting of all adverse events including serious adverse events (SAE), suspected unexpected serious adverse reactions (SUSARs), serious adverse drug reactions (SADRs) to the competent authority and independent ethics committee/institutional review boards based upon federal regulations and local/IRB policies.

[name], the sponsor-investigator, will report to Novo Nordisk all SAEs, SUSARs, and SADRs at the same time such events are reported to regulatory authorities or within 15 days from the sponsor-investigator becoming aware of such adverse events, whichever comes first.

[name] or his designee will collect the following information at minimum for each of these events:

1. Study name
2. Patient identification (e.g., initials, sex, age)
3. Event (preferably a diagnosis)
4. Drug
5. Reporter identification (e.g., Name, or initials)

Also 6) Causality, and 7) Outcome might be reported.

Definitions

Adverse Event (AE):

An AE is any undesirable medical event occurring to a subject in a clinical trial, whether or not related to the trial product(s). This includes events reported from the first trial related activity after the subject has signed the informed consent and until completion of the trial. Unexpected AEs as referenced in the US Norditropin® prescribing information.

Clinical Laboratory Adverse Event:

A clinical laboratory AE is any clinical laboratory abnormality regarded as clinically significant i.e., an abnormality that suggests a disease and/or organ toxicity and is of a severity, which requires active management, (i.e., change of dose, discontinuation of trial product, more frequent follow-up, or diagnostic investigation).

Serious Adverse Event (SAE):

A serious AE is an experience that at any dose results in any of the following:

- Death

- A life-threatening* experience
- In-patient hospitalisation or prolongation of existing hospitalization
- A persistent or significant disability/incapacity
- A congenital anomaly/birth defect
- Important medical events that may not result in death, be life-threatening*, or require hospitalisation may be considered an SAE when, based upon appropriate medical judgement, they may jeopardise the subject and may require medical or surgical intervention to prevent one of the outcomes listed in this definition.
- Suspicion of transmission of infectious agents

*The term life-threatening in the definition of SAE refers to an event in which the subject was at risk of death at the time of the event. It does not refer to an event which hypothetically might have caused death if it was more severe.

Serious Adverse Drug Reaction (SADR):

An adverse drug reaction (ADR) is an adverse event (AE) for which a causal relationship to the trial product is at least possible i.e., causal relationship is conceivable and cannot be dismissed. Serious adverse reaction (SAR): Adverse event which fulfils both the criteria for a Serious Adverse Event and the criteria for an Adverse Reaction.

Suspected Unexpected Serious Adverse Reaction (SUSAR):

An SAE which is unexpected and regarded as possibly or probably related to the trial/study product by the investigator.

Medical Events of Special Interest (MESI): A MESI is (1) a medication error (e.g., wrong drug administration or wrong route of administration) or (2) a suspected transmission of an infectious agent via the product.

Non-Serious Adverse Event:

A non-serious AE is any AE which does not fulfil the definition of an SAE.

Severity Assessment Definitions:

- Mild: Transient symptoms, no interference with the subject's daily activities
- Moderate: Marked symptoms, moderate interference with the subject's daily activities
- Severe: Considerable interference with the subject's daily activities, unacceptable

Relationship to study medication Assessment Definitions:

- Probable: Good reasons and sufficient documentation to assume a causal relationship
- Possible: A causal relationship is conceivable and cannot be dismissed
- Unlikely: The event is most likely related to an etiology other than the trial product

Medical Dictionary for Regulatory Activities (MedDRA) will be used for coding adverse events.

Outcome Categories and Definitions:

- Recovered: Fully recovered or by medical or surgical treatment the condition has returned to the level observed at the first trial related activity after the subject signed the informed consent
- Recovering: The condition is improving, and the subject is expected to recover from the event. This term should only be used when the subject has completed the trial.
- Recovered with sequelae: As a result of the AE, the subject suffered persistent and significant disability/incapacity (e.g., became blind, deaf, paralysed). Any AE recovered with sequelae should be rated as an SAE.
- Not recovered
- Fatal
- Unknown

Collection, Recording and Reporting of Adverse Events

All events meeting the definition of an adverse event must be collected and reported from the first trial related activity after the subject has signed the informed consent and until completion of the trial.

Follow-up of Adverse Events

[name], the sponsor-investigator, and Cincinnati Children's Hospital Medical Center will provide adequate medical care to the study subject for any study-related adverse events, including clinically significant laboratory values related to the study. This medical care for study subjects will be provided regardless of their insurance status.

All adverse events classified as serious or severe or possibly/probably related to the trial product will be followed until the subject has recovered and all queries have been resolved.

Pregnancy

Subjects will be instructed to notify the sponsor-investigator immediately if they become pregnant. [name], the sponsor-investigator, will report to Novo Nordisk any pregnancy occurring during the trial period.

Precautions/Over-dosage

All subjects will receive appropriate education about proper administration of medication from a trained medical professional. The subject's parent will be required to demonstrate proper technique and dosing prior to distribution of medication. They will be asked to notify the study team in case of an overdose and the PI will determine if further medical monitoring is needed based on the described event.

